#### 6.2.4 Follow-up Visits

##### Overview of Study Visits:

All study visits will be conducted via Zoom video and password protected REDCap surveys rather than in person. Study visits are outlined below:

- Consent and Screening Session (1 hours)
- Baseline Assessment Session (1.5 hours)
- 8-week visit assessment (1 hour)
- 16-week visit assessment (1 hour)
- 24-week visit assessment (1 hour)
- Oral fluid toxicology screens will be conducted at least once every two weeks during the study and will be entered into REDCap by study staff
- Weekly monitoring surveys will be collected monitoring substance use and Weekly Mindfulness Practice Diary

##### **Participant Communication**

Study staff will conduct outreach phone calls every two weeks during the 6-month study. If a participant does not respond to the phone call and has not been responsive within the past two weeks, study staff will reach out using e-mail, text message, or private message via Facebook or Instagram. Phone number, e-mail address, social media handle, and the names and contact for three close contacts will be recorded in the demographics survey outlined in the participant consent form. We will also collect the name and phone number of the patient's buprenorphine prescriber in the demographics survey. The prescriber would only be contacted in case of emergency or potentially life-threatening adverse event relating to the patient.

According to Mitchell *et al*, sending private messages via text or Facebook was a more effective way of communication with SUD participants than leaving voicemails. Only private, direct messages will be sent to participants through private social media messaging. The voicemail, text, email, and social media outreach attempts will be limited to scheduling and general content and will not include any mention of the research study or the nature of the study. Study participants will be contacted through the “Stress Reduction Study” Facebook and Instagram accounts.

Only secure WiFi will be used to communicate with participants. If a study staff member’s home WiFi is not password protected, they will be required to use a study phone. Only a CHA IT approved secure study cell phone and computer, both password-secured, will be used to communicate with participants. All communication will be logged in a G-suite secure study call log, and messages will be deleted from the study cell phone or social media site once logged in the call log.

#### 6.2.5 Completion/Final Evaluation

Final primary outcome/endpoint is number of biochemically confirmed oral fluid toxicology opioid negative abstinent periods (two-week periods of opioid abstinence during weeks 13-24 of the study defined as the number of biochemically confirmed illicit opioid negative abstinent periods (defined by negative oral fluid tests (negative for opiate, oxycodone, fentanyl, methadone) AND no self-reported illicit opioid use) during weeks 13-24 of study.

Final study session is week 24 and all the evaluation measures and assessment batteries that happen within two weeks of that day. Please refer to schedule of evaluations for an exact list of assessments used in this session.

#### Participant Reimbursement:

Participants will be paid using either anonymous, retail, online reward cards, OR anonymous, HITECH safe reloadable prepaid cards. Specifically, these online reward cards would be provided through a company like Tango (<https://www.tangocard.com>), a HIPAA compliant rewards service, or Comdata, a CHA approved reloadable gift card vendor. Use of Tango will require the input of participant email. Use of anonymous, retail, non-reloadable prepaid cards will not require any participant information to be recorded.

Participants will also be rewarded with a completion bonus for an oral fluid screen completion rate of at least 90%, completion of baseline, 8-week, 16-week, and 24-week assessments, and completion of more than 75% of weekly surveys. If assigned a study phone, the participant must also return this phone to be eligible to receive this bonus. Participants will receive an email notification for each weekly gift card they receive.

For completing baseline, 8-, 16-, and 24-week survey batteries within 48 hours of their assignment, participants will be rewarded with \$5.

Payment will be given as follows:

- \$20 at the Screening/Consent visit for completion of screening
- Up to \$45 at Baseline Visit for completion of baseline visit
- \$5 per group attended (\$120 total)
- \$5 per bi-weekly period in which all assigned weekly surveys and oral-fluid toxicology screens are complete (\$60 total)
- Up to \$45 at 8 Week Assessment
- Up to \$45 at 16 Week Assessment
- Up to \$45 at 24 Week Assessment
- Up to \$48 for 24-week completion bonus if participants complete at least 90% of their randomly assigned oral fluid screens weeks AND complete 75% of weekly surveys between weeks 1 and 24. If assigned a study phone, the participant must also return this phone to be eligible to receive this bonus. This bonus could range from \$36 to \$48 depending on how many weekly surveys are completed (\$2 for each weekly survey completed).
- \$50 for completing an optional M-ROCC or control completer qualitative interview (available for first 30 completers).
- **Up to \$478 total**

Study Payments will be given the following times:

Payment 1: \$20 for Screening/Consent visit

Payment 2: Up to \$45 at Baseline survey/computer visit

Payment 3: Up to \$45 at 8 Week Assessment

Payment 4: Up to \$45 at 16 Week Assessment

Payment 5: Up to \$143 at 24 Week Assessment

Weekly Payments: Up to \$180 spread out across 24-weeks. Participants will be able to choose whether they receive these payments each time they are earned, or at the end of each large survey battery.

### 6.2.6 Qualitative Interviews

We will conduct a minimum of 12 and a maximum of 30 qualitative interviews of M-ROCC or control group completers, defined as having attended at least 3 LDM sessions and 12 MTPC-ODU/MCS sessions or 15 control sessions of a possible total of 24 sessions. Interviews will be conducted with a minimum of 6 and a maximum of 15 participants from each study arm. Interviews will last between 30 and 60 minutes. All completers will be invited to interview until thematic saturation is reached. Interviews will be conducted on the HIPAA-compliant videoconferencing technology platform Zoom. Research staff with qualitative interviewing experience will be trained to conduct productive post-study interviews, oversee preparation of transcripts and ensure compatibility for it to be entered into the software program ATLAS.ti version 8.4.4 to enable comparison across qualitative data sources.

The M-ROCC qualitative interviews will be structured to identify:

- 1) Themes regarding online mindfulness delivery.
- 2) Challenges of online group delivery
- 3) Strengths of online group
- 4) Subjective experience of the online supervised oral fluid testing process
- 5) Benefits of group-based approach to treatment, hypothesizing that reasons for mindfulness group retention will also include mindfulness practice benefits, body awareness, emotion regulation, acceptance of medication, and values clarification.

The control group qualitative interviews will be structured to identify:

- 1) Themes regarding online GBOT delivery, such as shared identity, accountability, and supportive community.
- 2) Challenges of online group delivery
- 3) Strengths of online group
- 4) Subjective experience of the online supervised oral fluid testing process.
- 5) Benefits of group-based approach to treatment, hypothesizing that group-based treatment creates an atmosphere of mutual identification and acceptance in which participants gain support and inspiration through positive role modeling.

Analysis of the qualitative data obtained through these interviews will begin with transcription. The text output from the qualitative interviews will be generated using Transcription Star transcription services (<https://www.transcriptionstar.com/>), an online service provider that specializes in HIPAA compliant audio transcription. To protect human subjects' privacy, only the audio (mp3) files from qualitative interviews will be sent to Transcription Star. The study staff will only record and download interview data

using a desktop computer at the CMC office in order to ensure that the interview files are securely maintained. Files will be downloaded to the secure CHA server before being de-identified and uploaded to the secure G-Drive. Study staff will anonymize the mp3 files (using Audacity) by removing any identifiers mentioned during the interview. Audacity has been previously approved by the CHA IT department, and only saves files locally. The qualitative interviews will be converted from video mp4 format to audio mp3 format using Zoom HIPAA compliant conversion software. Audio recordings in mp3 format will be uploaded to transcriptionstar.com and will be securely stored and transmitted using HTTPS and Transport Layer Security (TLS) 1.2 encryption, which is the highest level of security available. Once the transcriptions are complete, the text of the transcripts will be checked against the digital recordings and errors will be corrected. The transcripts will then be prepared as rich text format files for compatibility with the computer software, ATLAS.ti, version 8.4.4. In addition, other data sources will also be entered by research staff into ATLAS.ti to enable comparison across qualitative data sources.

The transcriptions of the interviews will be coded using two approaches simultaneously: 1) coding using revised a priori codes based on the themes described above; and 2) open coding to identify new concepts found in the data. Trustworthiness of the data will be determined through investigator meetings, the application of analytic reflexivity in the interpretive process, and constant comparison of emerging themes. To refine themes, the team will further analyze all excerpts within a theme into sub-categories as well as define and name themes. Finally, qualitative themes and results in the primary care implementation pilot will be compared.

## **7. SAFETY ASSESSMENTS**

AEs will be systematically assessed at each assessment visit (weekly surveys, baseline, 8, 16, 24). In addition, group leaders and research coordinators will be trained to identify and report any adverse events that may occur or are reported during weekly live-online group visits. All AEs will be reviewed weekly by the Senior RC and the MINDFUL-OBOT Clinical Director, and monthly by the PI, and SAEs will be reviewed by PI within 24 hours. Please see adverse events section (7.3) below.

### **7.1 Specification of Safety Parameters**

Participants are assessed regularly for AEs, hospitalization, and changes in medication.

## 7.2 Methods and Timing for Assessing, Recording, and Analyzing Safety Parameters

### **a.**

#### 7.2.1 Expected Risks

##### **1. Worsening of underlying illness**

People with OUD are at high risk of worsening of the underlying disorder, which can lead to opioid overdose, intoxication, life-threatening accidents, inpatient hospitalization for detoxification or stabilization, and death. Given the high rate of relapse and overdose death both in this population of patients with OUD, inpatient hospitalization for opioid use disorder and overdose death are both risks that are expected to occur to the study but will be unlikely to be related to the protocol. Co-morbid psychiatric disorders are common, especially PTSD, MDD, Bipolar Disorder, Anxiety disorders, and OCD. Worsening of underlying mental illness may also occur, which would be an expected adverse event. Suicidality is a common symptom in this population and suicidal ideation is an expected symptom as a sign of worsening of underlying mental illness or opioid use disorder. Non-life threatening suicide attempts associated with an overdose, or any non-life threatening, self-harm among patients with prior suicidality, self-harm, past suicide attempts, or other risk factors would be an expected risk of the study. However, if a participant without previous suicidality, previous self-harm, or other risk factors were to attempt to commit suicide or physically harm themselves, then this would be unexpected. Life threatening suicide attempts are an unexpected events. Medical events related to injection, inhalation or other methods of administration of opioids and other drugs of abuse can also happen and would be expected risks in this population.

##### **2. Time spent learning mindfulness techniques**

Participants will be invited to practice mindfulness skills and techniques at home, which may involve negotiating with those at home to create time and space for practice. This will not be required of them.

For #3 and #4 below, research coordinators, group leaders, and the PI will be trained to respond to escalating anxiety, psychosis, or any other worsening psychiatric symptoms. They will be trained to alert the buprenorphine prescriber or their delegate (e.g. nurse care manager) by phone/page or electronic medical record (within participating healthcare systems) within 24 hours of becoming

aware of the escalating symptoms, and to contact the CMC Medical Director or Principal Investigator by phone or page as soon as possible and at most within 24 hours of alerting the existing care provider (s) to review the case. The care team and study staff will work together to determine the appropriate referral, including referral to outpatient mental health and/or local Emergency Department if necessary.

### **3. Increased anxiety due to difficulties in mental training program**

Mindfulness practices can sometimes cause anxiety for those who practice. Support from the Group Leader and the group can help participants recognize that this anxiety is part of the process and can help people learn to manage these feelings. If meditation and mental exercises are causing a worsening of anxiety for participants, they will be encouraged within groups to change their approach to the practice. Research coordinators will assess for worsening symptoms every two weeks during the engagement call adverse events report, and also during each live-online group session. If the participant(s) are unable to find a way to practice without eliciting an increase in symptoms, then they may be asked to stop practicing and to meet with either the M-ROCC Clinical Director, the CMC Medical Director, or the Principal Investigator for an evaluation. The participant may ultimately be terminated from the study if they are experiencing an adverse reaction. These participants may continue to receive other treatments at their primary care site as part of their ongoing treatment plan.

- 4. In some very rare cases, meditation practice can lead to a dissociative state or to psychosis.** This is more likely in participants with current conditions of or a predisposition to psychosis. Participants experiencing active psychosis are excluded from participating in this study. If a participant begins to experience these feelings during his or her time in the study, then the study staff and care team will work together to alert the appropriate care team providers and study investigators immediately. The participant may be asked to stop practicing and to meet with either the CMC Medical Director or the Principal Investigator for an evaluation in person or via videoconference while a member of the study staff is onsite with the person. Videoconferencing will occur through the HIPAA compliant and encrypted communications platform zoom. The participant may ultimately be terminated from the study if he or she is experiencing an adverse reaction. These participants may continue to receive other treatments at their primary care site as part of their ongoing treatment plan. If the participant experiences a dissociative state or psychosis during a group session, the research coordinator and/or group leader will ask the participant to meet with them

individually in an online breakout room, while the other/group leader continues on with the session and will contact the appropriate care provider(s).

5. **Physical discomfort due to gentle movement aspect of training.** The training will involve gentle movements and stretching. Some participants could experience physical discomfort during this aspect of training. If a participant feels discomfort, he or she will be encouraged to engage in a less straining manner. If discomfort continues, then the participant will be asked to sit out of this brief element of training and discuss the areas of discomfort with their PCP before return to practice of physical postures. Severe discomfort is not expected, but could possibly occur. In this case, the participant will be treated for this pain, and encouraged to return to practice stationary forms of mindfulness. If a participant gets hurt or get sick as a direct result of being in this study, emergency treatment will be given to them. All needed emergency care is available to participants, just as it is to the general public. Cambridge Health Alliance has not set aside any money to pay for a research-related injury or illness.
6. **Feelings of embarrassment or anxiety when asked personal survey question.** Some survey questions are of a sensitive or personal nature and may cause the participant to become upset. In some rare cases, participants may require mental health support upon feeling upset by the survey questions. A participant's referring clinician will be contacted if the participant needs additional mental health support. The PI, M-ROCC Clinical Director, and CMC medical director will remain available to field questions from participants about their experience with mindfulness and any adverse experiences. The clinical director will help to monitor participants and work with the referring clinician to coordinate behavioral health care for participants.
7. Monitoring may lead to anxiety and difficulty with completion of interviews may lead to feelings of guilt or shame. Staff will specifically be trained not to shame anyone about missed sessions, but instead focus on what they can do to complete the next ones.
8. Despite efforts to prevent data breaches, any use of electronic devices and internet data transmission can result in a **breach of confidentiality**.
9. Group members will be asked to keep what others share confidential, but they may not. As a result, **some private information may be disclosed** by other group members.

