### **3. STUDY DESIGN**

This will be a RCT comparing the efficacy of 24-weeks of a live-online Mindful Recovery Opioid Care Continuum (M-ROCC) group with 24-weeks of a live-online control group. Participants will be recruited from 3 affiliated sites from collaborating institutions that offer primary care office-based opioid treatment, in addition to 2 affiliated with CHA (see figure 1), as well as from OBAT sites in US states approved by the IRB for recruitment, and through Facebook and Instagram advertisements. The 3 non-CHA sites will execute SMART IRB reliance agreements with CHA and will not engage in study activities until their corresponding reliance agreements have been executed. We will enroll patients prescribed buprenorphine into a study that will be run remotely with assessments that can be completed fully online. Each study group will include patients prescribed buprenorphine. We will primarily recruit from various different primary care buprenorphine practices. Participants from various recruitment sites will come together for the live-online study groups. M-ROCC and live-online control groups will not replace standard of care at any sites and will instead be conducted as research groups.

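### Section 7.2.1's response to psychiatric worsening conflicts with remote conduct (evaluation of psychosis or dissociation) and with section 6.2.4 (when the prescriber may be contacted)

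*Combined protocol and SAP*

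**What the plan says.** **Evaluation of dissociation or psychosis.** Section 7.2.1 item 4 says such a participant may be asked to stop practising and to meet the CMC Medical Director or the PI for an "evaluation in person or via videoconference while a member of the study staff is onsite with the person". Item 3, on anxiety brought on by practice, asks the participant "to meet with either the M-ROCC Clinical Director, the CMC Medical Director, or the Principal Investigator for an evaluation" and sets no condition on how the meeting is held.

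**Conduct of the trial.** Section 3 describes "a study that will be run remotely with assessments that can be completed fully online". Section 6.2.4 states: "All study visits will be conducted via Zoom video and password protected REDCap surveys rather than in person". Inclusion criterion 2 in section 4.1 lists 16 states of residence.

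**Prescriber contact.** The paragraph placed before items 3 and 4 of section 7.2.1, which says it applies to both, covers rising anxiety, psychosis and any other psychiatric deterioration. It says of coordinators, group leaders and the PI: "They will be trained to alert the buprenorphine prescriber or their delegate", within 24 hours of learning of the symptoms. Section 6.2.4 (Participant Communication) says: "The prescriber would only be contacted in case of emergency or potentially life-threatening adverse event relating to the patient". Section 4.3 gives the same narrow purpose when the prescriber's details are collected. Section 7.5 has the PI notified of every adverse event within 48 hours and then decide what to do, with contacting the prescriber as one option.

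**Timing.** Under the same lead-in, staff must reach the Medical Director or PI as soon as they can and "at most within 24 hours of alerting the existing care provider". Item 4 has study staff and the care team "work together to alert the appropriate care team providers and study investigators immediately".

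**The concern.** Section 7.2.1 lists these events among the expected risks and links them to the mindfulness practice being tested, so the instructions for responding to them need to work for every randomised participant and to agree with the rest of the protocol.

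Two of them do not. If an investigator decides to evaluate a participant with new psychosis who lives far from study staff, neither listed route is explained for that participant, and videoconference without staff present is not listed. If a participant's anxiety escalates without becoming an emergency, a coordinator following section 7.2.1 alerts the prescriber and a coordinator following section 6.2.4 does not. What is done then depends on which page is consulted. An alert may be missed, or a disclosure made outside the purpose for which the contact details were collected. Whether staff complied or deviated also cannot be judged when two rules point in opposite directions.

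**Working it through.** There is no sample size, power or error-rate figure to reproduce. The check compares current sections, counts the eligible states and adds two sequential time limits. The revision history is not relied on.

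**1. Evaluation routes against remote conduct**

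| Input | Source | Content |
|---|---|---|
| Route A, psychosis or dissociation | 7.2.1 item 4 | In person |
| Route B, psychosis or dissociation | 7.2.1 item 4 | Video, with study staff beside the participant |
| Anxiety from practice | 7.2.1 item 3 | No condition on format |
| Conduct | 3 and 6.2.4 | Remote; visits by Zoom and REDCap |
| Residence | 4.1, criterion 2 | MA, CT, FL, ME, NH, NY, RI, TX, VT, CA, NC, VA, AL, AZ, IL, MI = 16 states |

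Routes A and B both require physical presence. No section describes sending staff to a participant or bringing a participant to staff. Item 4's own in-session step is an online breakout room, so one item mixes remote and on-site assumptions. The mismatch is confined to item 4.

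**2. When the prescriber is contacted**

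| Source | Trigger | Who decides |
|---|---|---|
| 7.2.1 lead-in to items 3 and 4 | Any escalating psychiatric symptom | Trained staff, within 24 h, before the Medical Director or PI need be reached |
| 6.2.4, and the purpose given in 4.3 | Emergency or possible threat to life, and nothing else | Not stated |
| 7.5 | Adverse event, after notification | PI |

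Applied to two cases:
- *New psychosis judged an emergency:* the lead-in requires contact and section 6.2.4 permits it. No conflict.
- *Escalating anxiety from practice, not an emergency:* the lead-in requires contact, section 6.2.4 excludes it, and section 7.5 makes it discretionary. The lead-in and section 6.2.4 cannot both be followed.

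**3. Time limits for psychosis**

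- Lead-in: up to 24 h to alert the prescriber, then up to 24 h more to reach the Medical Director or PI. Outer limit = 24 h + 24 h = 48 h from awareness.
- Item 4: immediately, to providers and investigators.
- Section 7.5: PI told of any adverse event within 48 h of its being reported, the same length as the lead-in's outer limit.

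Immediate notification satisfies all three. The text gives different limits for one event, but no one is prevented from complying.

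**The case against.** The case against giving this much weight is substantial.

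- The onsite condition is a single clause about events the protocol calls very rare, and the evaluation is something a participant may be asked to attend, not a mandatory step. This stands. It narrows the point but does not remove it: once an evaluation is wanted, no workable route is described for a distant participant.
- Most of the response works remotely: alerts by phone or page, referral to outpatient care or a local emergency department, and the online breakout room. Active psychosis is excluded at entry, adverse events are assessed weekly, and engagement calls are made every two weeks. This also stands, and participants are not left without protection.
- Section 6.2.4 allows prescriber contact in an emergency, which can reasonably include new psychosis. This stands, so the contradiction is firm only for non-emergency worsening.

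A reader might go further and infer that the psychiatric response as a whole cannot be carried out, or that most participants have no route to evaluation. The documents do not support either reading. Item 3 sets no onsite condition, and no distribution of participants by state is given. Section 4.3 says recruitment is primarily from five named sites across CHA and three other institutions, with up to 50 further Massachusetts sites and other sources. Sixteen eligible states do not show that most participants are distant.

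A reader might also infer that the time limits are impossible to meet together. They are not, as step 3 of the working shows. The suicide-risk text in section 7.6 covers a different event, itself calls for immediate contact during groups, and adds nothing to the timing point.

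**Conclusion.** The point holds in two parts, with one secondary clarification.

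1. Item 4's evaluation routes do not fit a remotely conducted trial for participants away from study staff. The number affected cannot be derived from the documents. This rests on there being no undescribed arrangement for onsite presence.
2. For non-emergency psychiatric worsening, prescriber contact is required by the section 7.2.1 lead-in, excluded by section 6.2.4 and discretionary under section 7.5. This is a direct contradiction and reaches both items 3 and 4 whenever the event is not an emergency.
3. For psychosis, the stated limits for reaching an investigator run from immediately to 48 hours. This is an inconsistency, not an impossibility.

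The matter concerns safety procedure. It has no bearing on the primary outcome, the sample size or the analysis. It should be fixed, because the subject is participant safety and a wording change can do it, but it does not undermine the trial.

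**What to change.** The sponsor's clinicians should reconcile section 4.3 (purpose of the prescriber's contact details), section 6.2.4 (Participant Communication), section 7.2.1 (lead-in and items 3 and 4) and section 7.5 into one statement that gives, for each kind of event, who is told, by whom and within what single time limit. The other sections should then refer to it. They should also reconcile item 4's evaluation routes with remote conduct, so that the text says what applies to a participant who is not near study staff.

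Which contacts, limits and evaluation format are right is for those clinicians; none is proposed here. The cost is a protocol wording amendment. If the sponsor keeps a requirement for physical presence, the resources to meet it would be additional and cannot be costed from the documents.
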